## 1.2 Study design

This is an observational, prospective cohort study of patients  $\geq 50$  years old with a Herpes Zoster (HZ) diagnosis, carried out by a French national random sample of community first line practitioners concerned by HZ diagnosis: general practitioners (GPs), dermatologists and ophthalmologists.

Patients  $\geq 50$  years old with a primary HZ diagnosis (no earlier case of HZ) were included in the **HZ cohort** during a one-year inclusion period.

[figure not shown]
All patients of the HZ cohort presenting Post Herpetic Neuralgia (PHN) 3 months (defined as the presence of HZ-associated severe "worst" pain: pain  $\geq 3$  from ZBPI item "worst pain") after HZ rash onset symptoms were included secondarily in the **PHN cohort**.

Patients of the HZ cohort were followed-up for 3 months using phone interviews with a nurse at 1 month (+/- 3 days) and 3 months (+/- 1 week) after HZ rash onset.

Patients of the PHN cohort were followed up for another 6 months period using phone interviews with a nurse a 6 months (+/- 1 week) and 9 months (+/- 1 week) after HZ rash onset.

Page

Graph 1: Study Design

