### 1.3.2 *Physicians*

In the study of the General Practitioners' sentinel electronic surveillance network, the average yearly number of cases reported by each GP was 3.31 (95%CI 2.82; 3.80) (Gonzales Chiappe S, 2010).

For the Posther study, it was assumed that GPs and specialists would include at least a mean number of 1 and 2 subjects respectively, for an initial 6 months period. With this hypothesis, a random sample of 170 GPs, 20 dermatologists and 20 ophthalmologists could include 250 cases of HZ.

In cohort studies, some participating physicians are not active, especially with scarce patients such as HZ cases. Assuming a rate of two thirds of active participation, 210 GPs, 30 dermatologists and 30 ophthalmologists should be recruited.

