#### 4. GENERAL STATISTICAL APPROACH

All statistical analyses will be descriptive and will provide description of the data along with 95% 2-sided CIs.

The quantitative variables are summarized using the following parameters:

- Number of non-missing data,
- Number of missing data,
- Mean,
- Standard deviation,
- Median and first & third quartiles
- Minimum,
- Maximum.

The qualitative variables are summarized using the following parameters:

- Number of non-missing data,
- Number of missing data,
- Counts and percentages

Missing data or unknown responses are not counted in the percentages, but numbers of missing data are presented in the results tables.

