Acupuncturist	23.00	70% - 1€	https://www.ameli.fr/l-assurance-maladie/statistiques-et-publications/donneesstatistiques/professionnels-de-santeliberaux/honoraires/honoraires-taux-etmoyens.phpsource - 2014

The cost for radiologists, healers, magnetizers will not be valorized.

The cost of the inclusion visit is evaluated according to the specialty of the investigator: general practitioner, dermatologist, ophthalmologist.

The cost of each medical visit recorded through phone interviews is evaluated according to the specialty visited.

The medical visit costs for one patient are the sum of all the costs of the visits made by the patient by time frame.

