### 5.2.2.3 Costs analysis

The costs assessment will be made for patients with both interviews conducted at 1 month and at 3 months. The costs assessments of the PHN cohort at 6 and 9 months will be made for patients who have also both interviews conducted at 6 and 9 months.

For both approaches (societal and payer), direct medical costs and indirect costs will be summed from inclusion up to 3 months for the global HZ cohort. For the PHN cohort, costs will be summed from inclusion up to 6 months and from inclusion up to 9 months. For the PHN cohort, costs will also be summed from inclusion up to 3 months, for comparison to the rest of the global HZ cohort.

Means and 95%CI of the means will be estimated by a generalized linear model, with Gamma distribution and log as link function.

Histograms of the costs will be produced for the HZ cohort. Values of the costs obtained in the PHN cohort will be plotted patient by patient.

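### The 95% CI of mean cost ignores clustering of patients within the enrolling physician; the likely effect is small, and a clustered CI for the HZ cohort is a cheap improvement

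*SAP*

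**What the plan says.** Section 1.2 describes a cohort "carried out by a French national random sample of community first line practitioners concerned by HZ diagnosis", so the physician is the unit sampled and patients are nested within physicians. For enrolment, section 1.3.2 states that "it was assumed that GPs and specialists would include at least a mean number of 1 and 2 subjects respectively, for an initial 6 months", and that "a random sample of 170 GPs, 20 dermatologists and 20 ophthalmologists could include 250 cases of HZ".

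Section 4 promises a "description of the data along with 95% 2-sided CIs". For costs, section 5.2.2.3 adds: "Means and 95%CI of the means will be estimated by a generalized linear model, with Gamma distribution and log as link function". Neither section names a physician effect, a cluster-robust variance or a resampling of physicians. The precision tables in sections 1.3.1 and 1.4.2 use 1.96 × SD/√n with no design effect.

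On the cost components, section 5.1.4.1.2 states: "The cost of the inclusion visit is evaluated according to the specialty of the investigator". The fee is 23 EUR for a GP and 46 EUR for a dermatologist or ophthalmologist. Sections 3.3.1 to 3.3.3 record that the including physician prescribes treatment, may prescribe sick leave and may refer to a specialist. Sections 5.1.4.1.3 and 5.1.4.1.4 report no emergency visits and no hospital stays, so total cost consists of medications, visits and sick leave.

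**The concern.** Cost is the primary objective (section 1.1), and its CI is how the reader will judge the precision of the result. That precision has already fallen with the drop from 250 to about 100 patients (section 1.4.2).

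Two patients of one physician share the inclusion fee exactly. They may also resemble each other in drugs, sick leave and referrals. If so, they carry less information than two patients of different physicians, and an interval built on independent patients overstates precision. The direction is clear for any positive correlation. The size depends on how many patients each physician enrolled and how strong the correlation is, and the SAP gives neither.

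**Working it through.** **Step 1. Reproduce the plan's figure.** Relative half-width = 1.96 × (SD/mean)/√n. With n = 100 and SD = mean: 1.96 × 1/10 = 19.6%, as printed in Table 2. The other entries for n = 100 (4.9% to 39.2%) also reproduce.

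**Step 2. Formulas with clustering.**
- Weighted cluster size: m_w = Σm²/Σm, with m the patients per physician.
- Design effect: DE = 1 + (m_w − 1) × ICC.
- Corrected half-width = 19.6% × √DE.
- Actual coverage of the uncorrected interval = 2Φ(1.96/√DE) − 1.

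Table 2 uses a normal approximation. The factor √DE applies equally to the standard error of the log mean in the Gamma model.

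**Step 3. Cluster sizes.**
- *As planned* (section 1.3.2): 170 GPs with 1 patient and 40 specialists with 2 give 170 + 80 = 250 patients. m_w = (170 × 1 + 40 × 4)/250 = 330/250 = 1.32.
- *As expected after the shortfall* (assumption): 100 patients falling at random on the active two thirds of the 270 physicians to be recruited, that is 180. Under random allocation m_w ≈ 1 + 100/180 = 1.56. Using 180 rather than the 210 behind the figure of 250 cases makes the clusters slightly larger.
- *Concentrated enrolment* (scenario only): m_w = 3, close to the 3.31 cases per GP per year cited in section 1.3.2.

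**Step 4. Results** for n = 100 and SD = mean. The ICC is an assumption throughout.

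| m_w | ICC | DE | Half-width | CI should be wider by | Coverage of uncorrected CI |
|---|---|---|---|---|---|
| 1.32 | 0.05 | 1.016 | 19.8% | 0.8% | 94.8% |
| 1.32 | 0.10 | 1.032 | 19.9% | 1.6% | 94.6% |
| 1.32 | 0.20 | 1.064 | 20.2% | 3.2% | 94.3% |
| 1.32 | 0.30 | 1.096 | 20.5% | 4.7% | 93.9% |
| 1.56 | 0.05 | 1.028 | 19.9% | 1.4% | 94.7% |
| 1.56 | 0.10 | 1.056 | 20.1% | 2.7% | 94.4% |
| 1.56 | 0.20 | 1.111 | 20.7% | 5.4% | 93.7% |
| 1.56 | 0.30 | 1.167 | 21.2% | 8.0% | 93.0% |
| 3 | 0.05 | 1.10 | 20.6% | 4.9% | 93.8% |
| 3 | 0.10 | 1.20 | 21.5% | 9.5% | 92.6% |
| 3 | 0.20 | 1.40 | 23.2% | 18.3% | 90.2% |
| 3 | 0.30 | 1.60 | 24.8% | 26.5% | 87.9% |

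**The case against.** The strongest reply is that clusters of one or two patients leave almost nothing to correct. The table bears this out for enrolment that was roughly even. Several stronger readings are tempting, and the SAP does not support them.

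- **Twelve months of inclusion means 2 to 4 patients per physician.** A reader might double the six-month assumption of 1 and 2. But section 1.4.1 lengthened inclusion because recruitment was slow. Doubling over the planned 210 physicians would give 2 × 250 = 500 patients, against about 100 expected. An average of 2 to 4 would need only 25 to 50 enrolling physicians, a number the SAP nowhere gives. The same section widened the physician pool, which tends to spread patients out.
- **Inactive physicians imply large clusters among the active ones.** Section 1.3.2 does say: "In cohort studies, some participating physicians are not active, especially with scarce patients such as HZ cases". It uses this only to raise the number to recruit. Physicians who enrol nobody say nothing about how many patients the others enrol.
- **The physician's prescribing drives the cost.** The SAP does not say so. Section 5.1.4.1.1 costs drugs bought before inclusion and drugs the patient reports. Section 5.1.4.2 costs days actually missed, and section 5.1.4.1.2 costs visits actually made to any practitioner. The only item fixed by the investigator is the inclusion fee, and that varies by specialty rather than by individual physician. Influence on the rest is plausible but partial.
- **The cost CI is the study's only inference.** Section 4 plans CIs throughout, and section 5.2.2.2.2 plans Wilcoxon and McNemar tests and CIs for the EQ-5D-5L index.

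What stands is the omission itself and its direction. A reader also could not tell even from concentrated enrolment: the flowchart in section 5.2.1 covers which physicians included patients, but not how many patients each included.

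**Conclusion.** The point holds as a minor one. The planned CI of mean cost takes no account of the physician, and it is too narrow if costs are positively correlated within physicians. That material narrowing has occurred is not shown. The 1% to 8% range rests on an assumed ICC of 0.05 to 0.30 and on cluster sizes inferred from the recruitment plan. At its upper end, the nominal 95% interval covers about 93%. Widening of 5% to 26%, with coverage down to about 88%, requires concentrated enrolment, which the SAP neither reports nor rules out.

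**What to change.** In section 5.2.2.3, for the HZ cohort, keep the Gamma/log mean and compute its CI with physician as the cluster. Either use GEE with an independence working correlation and a small-sample-corrected sandwich variance, or a bootstrap that resamples physicians. With the independence working correlation the estimated mean is unchanged. Beside the cost table, report the distribution of patients per including physician, so that readers can see whether clustering matters.

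Leave the PHN cohort on the planned method and state the limitation. At the plan's 16% it would hold about 0.16 × 100 = 16 patients, too few for a stable cluster-robust variance.

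The cost is low. The link from patient to physician must already exist, because the inclusion visit is priced by the investigator's specialty. The small-sample correction or bootstrap needs some extra programming, and the CI will probably be slightly wider.

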## 6. DATA HANDLING CONVENTIONS

Wordings (clear text) will be standardized before analysis. The listings will be submitted to the coordinating center for validation before use in the analysis.

Missing month of dates will be considered as 06 for durations and intervals computations.

Missing days of dates will be considered as 15 for durations and intervals computations.

When the unit is year, the result will be divided by 365.25.

When the unit is month, the result will be divided by 365.25/12 (=30.4375).

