## 2. POPULATIONS

### 2.1 Patients' population

To be included in the HZ cohort, patients had to fulfill all the following criteria:

- Patients with a first visit for a diagnosis of HZ and who attend the clinic within two weeks of the start of HZ symptoms (defined as unilateral pain accompanied by a unilateral rash without alternative diagnosis)
- Without any history of previous HZ
- $\geq 50$  years old
- Who agree to participate and signed informed consent
- Able to understand the study, to complete self-administered questionnaires (alone or with the help of a relative) and to answer phone interviews

All patients of the HZ cohort presenting PHN 3 months after onset of the HZ rash onset should be included in the PHN cohort.

PHN was defined as the presence of HZ-associated severe pains:  $\geq 3$  of the ZBPI item "worst pain", completed during the phone interview of the patient at 3 months  $\pm 1$  week.

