#### 3.1 Inclusion visit

For each patient included in the HZ cohort, physicians had to fill a paper medical questionnaire with the following information collected during patient's visit:

- Inclusion criteria
- Date of visit
- Demographics: Gender, Month and Year of birth, Occupational status - HZ characteristics:
  - o date of HZ rash onset o prodromal symptoms Yes / No (prodromal pain, hyperthermia, malaise, other – specify) o rash localization (left side, right side): head, ophthalmic zona, HZ oticus, neck, chest, arm, forearm, hand, abdomen, pelvis, thigh, leg, foot
  - o complications Yes / No:
    - cutaneous: viral dissemination, bacterial surinfection, other - specify

- ocular: lost of corneal sensitivity, keratitis, scleritis, uveitis, iridocyclitis, other - specify
- neurological: transverse myelitis, meningo-encephalitis, paralysis of cranial nerve, paralysis of peripheral nerve, syndrom of Ramsay Hunt, persistance of HZ pain, other – specify
- visceral: extension of the viral infection (bronchitis, oesophagitis, cystitis,...), viral dissemination (pneumonia, arthritis, hepatitis,...), other - specify
- ear
- other – specify
- associated comorbidities (Yes / No):
  - emotional problems, stress, depression
  - alcoholism ○ tobacco consumption ○ diabetes
  - renal insufficiency / dialysis ○ hepatic pathology
  - hepatitis C under active treatment within 12 months before HZ diagnosis
  - VIH infection with a CD4 rate < 350/ $\mu$ l or past opportunistic infection or other manifestation of AIDS at time of HZ diagnosis
  - Cancer – Solid tumor (ongoing chemotherapy or radiotherapy, or active or metastatic disease within 6 months before HZ diagnosis)
  - Malignous hemopathies (ongoing chemotherapy or radiotherapy, or active or metastatic disease within 6 months before HZ diagnosis)
  - Organ transplant within 12 months before HZ diagnosis or for 12 months or more with an ongoing anti-rejection treatment
  - Hematopoïetic cells or bone marrow transplantation before HZ diagnosis or for 12 months or more with an ongoing anti-rejection treatment
  - Active auto-immune pathology under treatment ( $\geq$  5 mg/day or more of corticoids or immunosuppressors) within 12 months before HZ diagnosis: rheumatoid arthritis, ankylosing spondylitis, lupus erythematosus, psoriasis, Crohn's disease, ulcerative colitis
  - Other comorbidity – specify

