### 5. ANALYSIS OF PATIENT DATA

#### 5.1 Analysis variables

##### 5.1.1 Clinical Variables

All data collected by the investigator at inclusion are considered as clinical variables.

In addition, the following criteria are computed:

- Age: rounding to integer of number of months between month of birth / year of birth and month of visit date / year of visit date, divided by 12
- Age in classes: [50 – 60[, [60 – 65[, [65 - 70[, [70 – 80[, >=80 years old
- Time between start of rash and inclusion date (Days): (inclusion date – rash date) / 365.25
- Number of body sites of rash (number of sites ticked among head, ... feet)

- Total number of sites of rash (number of sites taking into account the side left or right) - Patient immunocompromised: if at least one of the following condition is met:
  - o Active auto-immune pathology under treatment ( $\geq 5$  mg/day or more of corticoids or immunosuppressors) within 12 months before HZ diagnosis
  - o VIH infection with a CD4 rate  $< 350/\mu\text{l}$  or past opportunistic infection or other manifestation of AIDS at time of HZ diagnosis
  - o Cancer – Solid tumor (ongoing chemotherapy or radiotherapy, or active or metastatic disease within 6 months before HZ diagnosis)
  - o Malignous hemopathies (ongoing chemotherapy or radiotherapy, or active or metastatic disease within 6 months before HZ diagnosis)
  - o Organ transplant within 12 months before HZ diagnosis or for 12 months or more with an ongoing anti-rejection treatment
  - o Hematopoïetic cells or bone marrow transplantation before HZ diagnosis or for 12 months or more with an ongoing anti-rejection treatment o Ongoing immunosuppressive treatment is Yes
  - o At least one treatment prescribed by investigator or declared as taken by patient at any interview amongst ATC class L04 (Immunosuppressants)

Other comorbidities recorded as free texts are standardized before analysis. Other free texts are standardized as well when necessary.

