### 6.2 Windows for time points

Phone interviews should be conducted at 1 month +/- 3 days, at 3 months +/- 1 week (and for PHN cohort at 6 months +/- 1 week and 9 months +/- 1 week).

Automatic emails and calendar were sent to the nurses in charge of phone interviews for optimal management.

Interviews conducted > 30 days before or after the theoretical date will be considered as missing.

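### For a partial rash-onset date, the June / day-15 convention ignores the two-week entry window and often gives an impossible rash-to-inclusion time; filling in the month may also void on-time interviews.

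*SAP*

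**What the plan says.** SAP section 6 (Data handling conventions) gives one rule for all dates: "Missing month of dates will be considered as 06 for durations and intervals computations", and "Missing days of dates will be considered as 15 for durations and intervals computations". It makes no exception for any date and sets no bound from the inclusion visit. Section 6.1 adds that missing data are not replaced, without saying how this relates to partial dates.

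Rash onset is one of the dates collected: section 3.1 lists the "date of HZ rash onset" on the physician's questionnaire. It is used in two places:

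- Section 5.1.1 derives the time from rash to inclusion as inclusion date minus rash date.
- Section 1.2 schedules "phone interviews with a nurse at 1 month (+/- 3 days) and 3 months (+/- 1 week) after HZ rash onset", and counts the 6- and 9-month interviews from the same origin.

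Eligibility in section 2.1 is limited to patients "who attend the clinic within two weeks of the start of HZ symptoms".

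Section 6.2 then states: "Interviews conducted > 30 days before or after the theoretical date will be considered as missing". Section 5.2.2.3 restricts the cost analysis to patients with both the 1-month and 3-month interviews. Section 2.2 defines the PHN cohort by the worst-pain answer at 3 months.

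**The concern.** The entry criterion already places rash onset within about two weeks of a known date, the inclusion visit. The generic rule ignores this and substitutes a fixed calendar position. Because inclusion was extended to 12 months (section 1.4.1), June has no special standing as a month of onset.

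Two things are at stake. The first is certain whenever a rash date is partial: the derived rash-to-inclusion time can be negative or longer than the entry criterion allows. The second is conditional. If the target date for each interview is computed from the imputed onset, an interview held on time may appear more than 30 days off and be discarded. The patient then leaves the cost analysis, which is the primary objective, and without a 3-month answer cannot be classified for PHN. About 100 patients are expected (section 1.4.2). At the 16% PHN rate assumed in section 1.3.1 that is about 16 PHN cases, so a single lost case would be 1/16, or about 6%, of that cohort.

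**Working it through.** **The plan's own figure.** The only computed number in section 6 is the month length: 365.25/12 = 30.4375. It reproduces. The point does not depend on it.

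**Inputs.**
- Imputation: month = 06, day = 15 (section 6).
- Allowed delay from symptom start to visit: 0 to 14 days (section 2.1).
- Interview windows: ±3 days at 1 month and ±7 days at 3, 6 and 9 months, from rash onset (section 1.2).
- Interview set to missing if more than 30 days from its target (section 6.2).
- Assumptions: rash starts with or after the first symptoms; every onset day of a 12-month year (2016 as an example) and every delay from 0 to 14 days equally likely; year known; day 31 becomes 30 when the month is set to June.

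**Formulas.** Shift = imputed onset − true onset. Derived time = inclusion date − imputed onset, taken in days. (The formula in section 5.1.1 divides by 365.25 although the variable is labelled in days; the plain difference is used here.) The derived time is impossible if it is below 0 or above 14.

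**Step 1: rash-to-inclusion time.**

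| Missing part | Shift (days) | Below 0 | Above 14 | Impossible |
|---|---|---|---|---|
| Day only | −16 to +14 | 23.0% | 27.9% | 50.8% |
| Month only | −184 to +152 | 41.5% | 50.3% | 91.8% |
| Both | −199 to +166 | 43.4% | 52.5% | 95.9% |

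(Sums differ by 0.1 in places through rounding.)

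Examples:
- Onset 1 March, visit 3 March, day missing: onset becomes 15 March, time = −12 days (true 2).
- Onset 28 March, visit 5 April, day missing: onset becomes 15 March, time = 21 days (true 8).
- Onset 10 October, visit 14 October, month missing: onset becomes 10 June, time = 126 days (true 4).

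**Step 2: interviews, if the target date moves with the imputed onset.** Apparent deviation = |true deviation − shift|; the interview is lost if this exceeds 30.
- Day missing: the largest shift is 16 days, so an interview inside ±7 days is at most 16 + 7 = 23 days off. None is lost. A loss needs a true deviation above 30 − 16 = 14 days. If interviews were spread evenly over the accepted ±30 days, 12.5% would be lost.
- Month missing, or both: about 83% of interviews held within ±3 or ±7 days are lost. For an interview exactly on target, the shift exceeds 30 days for 305 of 366 onset days; 305/366 = 83.3%.

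**Step 3: imputation confined to [inclusion − 14 days, inclusion].** The error is at most 14 days, so no derived time is impossible, and an interview within ±7 days is at most 14 + 7 = 21 days off and is kept. If only the month is missing, the window spans 15 consecutive days and no month is shorter than 28, so a given day number occurs in it at most once and the date is recovered. In the October example this gives 10 October and 4 days. In the first March example the overlap of window and month is 1 to 3 March, with midpoint 2 March and a time of 1 day.

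**The case against.** The strongest objection is that the rule may never be applied to a rash date. The physician records onset at a visit soon after it happened, and interviews booked to within days through automatic emails and a calendar (section 6.2) need an actual date. The SAP reports no partial rash dates. A known day with an unknown month is especially unlikely for so recent an event, and a missing month is what produces the 92% and 83%. This stands: the figures describe what happens when the rule is used, not how often it is used.

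Three stronger readings are tempting, and the document does not support them.

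- **That patients would become ineligible.** Section 3.1 has the inclusion criteria recorded at the visit, and section 2.2 defines the analysable population by criteria met. Nothing says eligibility is re-derived from imputed dates.
- **That any partial rash date would cost interviews.** With only the day missing, no interview held inside its window can be lost. And section 6.2 does not define the theoretical date. Section 1.2 points to rash onset as the origin, but if the date already in the nurses' calendar is used, or inclusion is the origin, imputation moves nothing.
- **That the convention is wrong wherever it is used.** Day 15 gives a possible onset in about half of cases, and a June onset with a known day is unharmed. Birth is collected as month and year (section 3.1), and mid-year is a sensible value for a missing birth month.

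The statement in section 6.1 that missing data are not replaced does not settle the matter, because section 6 explicitly fills in date parts.

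**Conclusion.** The point holds for the rash-onset date. The convention ignores a bound that the SAP itself supplies. When the date is partial, it gives an impossible rash-to-inclusion time in about 51% of day-missing cases and 92% of month-missing cases, under equally likely onset days and delays and with rash starting no earlier than first symptoms.

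The effect on interviews, and through them on the cost analysis and PHN classification, is conditional. It requires the target date to be computed from the imputed onset, and it comes almost entirely from the missing-month case. With only the day missing, it is limited to interviews already more than 14 days off target.

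The number of affected patients is unknown and may be small or zero. The case for changing the rule is that its error is avoidable from information already in hand, and the change is cheap.

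**What to change.** In section 6, exempt the rash-onset date from the June / day-15 rule and confine its imputation to the interval from inclusion date − 14 days to inclusion date:

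- Day missing only: take the midpoint of the overlap between that interval and the known month, with a stated rounding rule.
- Month missing only: keep the known day and choose the month that puts it inside the interval.
- Both missing: use inclusion date − 7 days.
- Known parts that cannot fit the interval: query the date and do not impute.

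Keep the existing convention for birth dates. In section 6.2, state the origin of the theoretical date and whether an imputed onset may move it. Report the number of partial rash dates, so that a reader can see whether the rule was used at all.

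The cost is a few sentences in the SAP and a short code change. No new data are needed, apart from any date queries.
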